## 1.4 Safety endpoints

Safety endpoints include all adverse events by standardized DIADS AE grading criteria, vital signs, and clinical laboratory tests from time of randomization until the patient completes their study participation.

## 1.5 Randomization scheme

Patients will be randomized in a 1:1 ratio to the treatment and control arms. Randomization will be stratified by age ( $\geq 50$  and  $< 50$  years old) and sex.

# 2 ANALYSIS PLAN

## 2.1 Analysis populations

The intent-to-treat (ITT) population will include all randomized patients. Patients will be analyzed according to their assigned treatment arm. All efficacy analyses will be completed in the ITT population.

The as-treated population will include all randomized patients. Patients will be analyzed according to the treatment actually received.

## 2.2 Descriptive analyses

Descriptive statistics (proportions for categorical variables, means, medians, standard deviations and interquartile ranges for continuous variables) will be reported for all key patient variables, including baseline and demographic characteristics, use of medications, compliance, and study completion status. Data that are missing on key patient characteristics and the outcome will be fully described, including any patterns of missingness (i.e., any relationships between missingness of a variable and patient characteristics).

A CONSORT diagram displaying the number of patients screened, eligible, and consented along with reasons for ineligibility will be provided. Graphical tools such as histograms, boxplots, and scatterplots will be created to assess quality of data and to display patterns over time.

All tests will be performed at the alpha = 0.05 level of significance unless otherwise noted.

### **2.3 Primary efficacy analysis**

Time until shedding cessation will be compared between the two treatment arms using a two-sided Cox proportional hazards model adjusted for age and sex. The test will be performed at the alpha = 0.05 level of significance. The hazard ratio for shedding cessation will be estimated, along with its 95% confidence interval, from a Cox proportional hazards model. If the proportional hazards assumption is not met, we will consider an extended Cox model that relaxes the proportional hazards assumption.

The distribution of shedding cessation will be estimated using the Kaplan-Meier method, and Kaplan-Meier curves will be presented for each treatment arm. Time to shedding cessation at the end of the study period along with 95% confidence intervals will be presented for each treatment arm.

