### **2.4 Secondary efficacy analyses**

Time to resolution of all symptoms will be defined as the time from randomization until the first study day in which no symptoms are reported. The distribution of time to resolution of symptoms will be estimated using the Kaplan-Meier method, and Kaplan-Meier curves will be presented for each treatment arm. Time to symptom resolution at the end of the study period along with 95% confidence intervals will be presented for each treatment arm. The hazard ratio for resolution of symptoms will be estimated, along with its 95% confidence intervals, from a Cox proportional hazards model adjusted for age and sex.

We will model SARS-CoV-2 viral load in oropharyngeal tests over time using a generalized mixed effects linear regression model with a random effect for study participant to account for correlation within a participant. Viral load with cycle threshold (Ct) values above the limit of detection will be calculated by substituting a Ct value of 42 into the equation  $10^{(Ct - 42) * 0.23}$  to derive viral load from Ct. A logarithmic transformation on viral load will be fit to treatment arm, time, armXtime, and adjusted for age and sex to account for therandomization stratification variables. The armXtime interaction term will allow us to assess whether the trajectory of viral load differs by treatment arm. Time will be defined as days from randomization and, depending on model fit, will either be modeled continuously or with a flexible approach allowing a non-linear trajectory for the change in viral load over time. Model fit will be assessed based on visual inspection of the residuals. Alternative transformations or generalized linear models with a link function besides the identity link will be considered if the model does not fit the data well.

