Area under the curve (AUC) will be defined by a single participant's logarithmic base 10 viral load from oropharyngeal tests collected on days 0, 1, 3, 5, 7, 10, and 14. AUC will be calculated by the trapezoidal rule, using exact times of collection of each OP swab. Multiple imputation using chained equations will be used to impute missing viral load data prior to AUC calculation. Five data sets will be imputed, and imputed values will be calculated using non-missing viral load on each of the 7 sample collection days, treatment arm, age, sex, and whether or not a participant was hospitalized. A pooled linear regression model will be fit to log-transformed AUC as a function of treatment, age, and sex using the 5 imputed data sets. Difference in AUC by treatment arm and corresponding 95% confidence intervals will be reported using Rubin's Rules. The difference in AUC by treatment arm will also be done after refitting the model without participants who were hospitalized to assess sensitivity of results.

The incidence of hospitalizations and emergency department visits will be estimated for each arm, with 95% confidence intervals.

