## 2.7 Effect modification, subgroup, and sensitivity analyses

A subgroup analysis will be performed for the primary endpoint using only patients who present with symptoms at baseline.

A statistical interaction term between treatment arm and the following baseline characteristics will be added to the Cox proportional hazards model to test for effect modification.

- 1) CT value < 30 from the baseline OP swab,
- 2) presence of antibodies as defined by presence of IgG antibodies to SARS-CoV-2 Spike Receptor Binding Domain (RBD) at baseline, as measured by ELISA. Samples are considered seropositive against RBD if their absorbance value was greater than the mean of plus four standard deviation (SD) of all negative controls (n=130),
- 3) number of risk factors or predictors for severe disease present at baseline (temp 99.5+, cough, or shortness of breath present at randomization [symptoms count as a single risk factor], age  $\geq$  60, male sex, Black race, Hispanic ethnicity, BMI  $\geq$  30, and lab values of baseline lymphocyte counts <1000 and baseline ALT  $\geq$  94),
- 4) age  $\geq$  50,
- 5) sex

A Wald test performed at the alpha = 0.05 level of significance will be used to test whether the effect modification is statistically significant. The sensitivity and effect modification analyses will be performed in other key endpoints as well.

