## 3 HANDLING OF MISSING AND CENSORED DATA

All efforts will be made to minimize instances of missing data. However, we expect some missing data will occur. Our analyses will assume data are missing at random. For the primary endpoint of time to shedding cessation, any participant who drops out prior to having two consecutive negative tests will be censored at their last positive test. Participants who have no post-randomization test results available or a single test result that is negative will be censored at day 1. Similarly, participants will be right censored for the time to symptom resolution or progression at the time when their last symptom questionnaire is completed. Participants who are asymptomatic at screening and never report symptoms thereafter will be considered to have met symptom resolution at study Day 1. For other missing data, we will use multiple imputation-based analyses. This approach will be applied to any analysis involving endpoints or key

variables where any missing data occurs in order to adhere to the ITT principle. Sensitivity to assumptions regarding missingness will be addressed through sensitivity analyses.

If more than 5% of participants do not have the time of shedding cessation observed (i.e. they are right-censored), we will perform a sensitivity analysis to evaluate the robustness of our findings to missing data assumptions. In the sensitivity analysis, among those missing timing of shedding cessation, we will assume varying proportions (e.g. 25%, 50%) of participants in each arm who would have ceased shedding by Day 28. The proportions will differ by arm so we can evaluate whether our findings stand if it were true that people who dropped out stopped shedding earlier in the placebo arm vs the active arm.

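### Adding the day-0 oropharyngeal Ct to the primary Cox model and the AUC regression would gain efficiency at little cost

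*SAP*

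**What the plan says.** The primary test in SAP 2.3, repeated in Protocol 12.3, is made "using a two-sided Cox proportional hazards model adjusted for age and sex". The AUC regression in SAP 2.4 models log-transformed AUC "as a function of treatment, age, and sex using the 5 imputed data sets". Age (50 and over, or under 50) and sex are the randomisation strata, and SAP 2.4 gives that reason for the viral-load mixed model, which is "adjusted for age and sex to account for therandomization stratification variables".

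The baseline measurement appears in three other places:

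- The AUC is built from "logarithmic base 10 viral load from oropharyngeal tests collected on days 0, 1, 3, 5, 7, 10, and 14", so day 0 is its first point.
- Day-0 load is among the variables in the AUC imputation: "Multiple imputation using chained equations will be used to impute missing viral load data prior to AUC calculation".
- SAP 2.7 lists "CT value < 30 from the baseline OP swab" as an effect modifier to be tested by interaction in the Cox model.

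Neither document enters day-0 Ct or viral load as a main-effect covariate in the primary or AUC treatment estimate.

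**The concern.** The primary endpoint is non-detection in the oropharynx, and day-0 Ct measures how far a patient stands from non-detection at that same site. Entry requires a positive molecular assay within 72 hours of the swab, with or without symptoms, so patients may start from very different loads. If baseline load predicts clearance time, leaving it out of the model gives up power for the primary test and precision for the AUC.

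The two planned uses of baseline data do not recover this. The Ct<30 interaction is a separate test on a dichotomised variable, and the mixed model has a different outcome.

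The stake is largest at the reduced effects that SAP 6 anticipates. There the plan's remedy is to enlarge the trial, or to stop it if more than 180 patients would be needed. This is an unused gain, not an error.

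**Working it through.** **The plan's own figure.** SAP 4.2 states 79 events for 80% power at HR 2.03, two-sided alpha 0.04999, 1:1. Schoenfeld's formula gives 4 × (1.96 + 0.84)² / (ln 2.03)² ≈ 63 events, and Freedman's gives 68. With 79 events, Schoenfeld power at HR 2.03 is 88%. At HR 1.8, 1.6 and 1.4 it is 74, 55 and 32%, against the 61, 41 and 22% in SAP 6. The stated figures therefore do not reproduce. That is a separate matter: the argument here uses only the contrast between two models fitted to the same simulated trials, not absolute power.

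**Distance to the endpoint.** SAP 2.4 uses 0.23 log10 per Ct and handles non-detects "by substituting a Ct value of 42 into the equation". A patient at Ct 20 is (42 − 20) × 0.23 = 5.06 log10 from non-detection. One at Ct 30 is (42 − 30) × 0.23 = 2.76.

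**Cox simulation, inputs from the documents.** 60 patients per arm; control median 14 days; visits on days 1, 3, 5, 7, 10, 14, 21 and 28; event at the first of two consecutive negatives; drop-outs censored at the last positive (SAP 3); others without the event censored at day 28.

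**Assumptions.** Exponential clearance given baseline load; 10% drop-out spread uniformly over 28 days in both arms; age and sex not prognostic; SD of log-hazard explained by baseline load of 0, 0.4 or 0.7 (hazard ratio per SD of 1.00, 1.49 or 2.01). The conditional HR was set so that the age/sex-only HR averages the same as at SD 0. There were 6,000 trials per setting.

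Power (%), age/sex only vs with day-0 Ct added:

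| Arm-level HR | SD 0 | SD 0.4 | SD 0.7 |
|---|---|---|---|
| 2.03 | 90.4 vs 90.3 | 90.5 vs 94.0 | 89.8 vs 97.2 |
| 1.8 | 76.5 vs 76.2 | 75.7 vs 80.8 | 74.8 vs 87.6 |
| 1.6 | 56.6 vs 56.6 | 55.5 vs 61.1 | 54.5 vs 69.3 |
| 1.4 | 33.1 vs 33.2 | 31.9 vs 35.5 | 30.8 vs 40.9 |

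The Monte Carlo SE of a difference is 0.15 to 0.7 points. The squared-z ratio is about 1.00, 1.14 and 1.40. In patients this is 120 × 0.14 ≈ 17 extra at SD 0.4 and 120 × 0.40 = 48 at SD 0.7.

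**Variations at HR 2.03 (SD 0 / 0.4 / 0.7).**
- Cut at the 79th event (4,000 trials): 87.8 vs 87.8, 87.5 vs 91.9, 87.4 vs 96.4%.
- If 2.03 is the HR conditional on baseline load: 90.5 vs 90.1, 84.9 vs 89.2, 73.7 vs 87.6%.
- Ct measured with reliability 0.7 (SD 0.4 / 0.7): 92.6 / 94.9% with Ct.
- 10% of Ct values missing and mean-filled (SD 0.4 / 0.7): 93.5 / 96.4% with Ct.

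**A weaker covariate.** At SD 0.2 (hazard ratio 1.22 per SD) the gain is about 1 to 3 points. One run near HR 1.6 gave 53.9 vs 56.7%. Another, cut at 79 events and tuned to about 80% power, gave 80.4 vs 81.7%.

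**Where the gain comes from.** The SE of the log HR at arm-level 2.03 rises slightly with adjustment: 0.2235 to 0.2251, 0.2245 to 0.2278 and 0.2265 to 0.2328. Power rises because the conditional log HR lies further from zero.

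**Type I error.** Null rejection over 20,000 trials at SD 0.4 and 0.7 is 5.2–5.3% without Ct and 5.4–5.5% with it.

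**AUC.** For days 0, 1, 3, 5, 7, 10 and 14 the trapezoid weights are 0.5, 1.5, 2, 2, 2.5, 3.5 and 2 (sum 14, sum of squares 33). With equal variances and constant within-person correlation r, the correlation of day 0 with AUC is

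(0.5 + 13.5r) / √(33 + 163r),

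and the interval width is multiplied by √(1 − correlation²).

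| r | Correlation with AUC | Interval narrower by |
|---|---|---|
| 0 | 0.09 | 0.4% |
| 0.1 | 0.26 | 4% |
| 0.3 | 0.50 | 14% |
| 0.5 | 0.68 | 26% |

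If correlation decays exponentially with the same mean, the last three rows become 3, 10 and 20%. On log-transformed AUC, simulated profiles give about 4, 13 and 24–25% (constant) or 3–4, 10–12 and 20–22% (decaying). All of these assume complete data.

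**The case against.** The planned models are sound. Adjusting for the stratification factors is standard, nothing is biased, and power at the planned effect is adequate. The benefit rests on a prognostic strength that the documents do not give, and SD 0.7 is a strong covariate. All of that stands, and it is why the gain is stated as a range from nothing upwards.

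The Cox runs also assume a single monotone, log-linear effect. Newly diagnosed asymptomatic patients are eligible, and some may still be rising, with low load but long shedding ahead. If the association reverses in 25% of patients (an illustrative assumption), the gain near HR 1.6 falls from 5.7 to 1.5 points at SD 0.4 and from 13.8 to 3.1 at SD 0.7. Eligibility does not require a positive oropharyngeal swab at day 0, so values may pile up at Ct 42, which the Cox runs do not model. These points shrink the gain but do not turn it into a loss.

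The estimand changes. The plan is sized on arm-level medians of 14 and 7 days, and the Kaplan-Meier curves are unadjusted, whereas the new HR is conditional on baseline load. This is a real cost and has to be stated in the SAP.

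Finally, the day-0 oropharyngeal swab is documented in the SAP only. The protocol's enrolment section lists no swab, its follow-up visits start at Day 1, and the schedule of events is not visible here. Its timing before dosing therefore needs confirming.

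**Conclusion.** The point holds as an efficiency improvement that the sponsor should make. At HR 1.8, 1.6 and 1.4 with 120 patients, adding day-0 Ct to the Cox model is worth nothing if baseline load is not prognostic, about 1 to 3 points of power at SD 0.2, 4 to 6 at SD 0.4 and 10 to 15 at SD 0.7. The largest loss seen in these runs is 0.4 points. The AUC interval narrows by 0.4% at zero correlation and by up to about 26% at a within-person correlation of 0.5. Confidence is medium, because prognostic strength and the shape of the association are assumed.

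**What to change.** Before unblinding:

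1. In SAP 2.3 and Protocol 12.3, add continuous day-0 oropharyngeal Ct (non-detect set to 42) alongside age and sex, and state that the hazard ratio is conditional on these. Using Ct itself avoids the printed Ct-to-load conversion in SAP 2.4, which rises with Ct and needs its sign checked.
2. In the SAP 2.4 AUC regression, add the day-0 value (Ct, or log10 load, which is linear in Ct) from each of the five imputed data sets.
3. SAP 3 says "For other missing data, we will use multiple imputation-based analyses". Add one exception: in the primary Cox model, a missing day-0 Ct is filled from baseline data only, for example with the overall mean.
4. State that the day-0 swab precedes dosing, unless the schedule of events already does.
5. Keep the age/sex-only model as a sensitivity analysis.

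The cost is wording in four sections; no new sample is needed. Three downsides remain. The conditional hazard ratio will not be what the unadjusted Kaplan-Meier curves display. The same missing day-0 value would be mean-filled in one model and multiply imputed in the other. The documents also do not say how many day-0 values will be missing.

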### **2.4 Secondary efficacy analyses**

Time to resolution of all symptoms will be defined as the time from randomization until the first study day in which no symptoms are reported. The distribution of time to resolution of symptoms will be estimated using the Kaplan-Meier method, and Kaplan-Meier curves will be presented for each treatment arm. Time to symptom resolution at the end of the study period along with 95% confidence intervals will be presented for each treatment arm. The hazard ratio for resolution of symptoms will be estimated, along with its 95% confidence intervals, from a Cox proportional hazards model adjusted for age and sex.

We will model SARS-CoV-2 viral load in oropharyngeal tests over time using a generalized mixed effects linear regression model with a random effect for study participant to account for correlation within a participant. Viral load with cycle threshold (Ct) values above the limit of detection will be calculated by substituting a Ct value of 42 into the equation  $10^{(Ct - 42) * 0.23}$  to derive viral load from Ct. A logarithmic transformation on viral load will be fit to treatment arm, time, armXtime, and adjusted for age and sex to account for therandomization stratification variables. The armXtime interaction term will allow us to assess whether the trajectory of viral load differs by treatment arm. Time will be defined as days from randomization and, depending on model fit, will either be modeled continuously or with a flexible approach allowing a non-linear trajectory for the change in viral load over time. Model fit will be assessed based on visual inspection of the residuals. Alternative transformations or generalized linear models with a link function besides the identity link will be considered if the model does not fit the data well.

Area under the curve (AUC) will be defined by a single participant's logarithmic base 10 viral load from oropharyngeal tests collected on days 0, 1, 3, 5, 7, 10, and 14. AUC will be calculated by the trapezoidal rule, using exact times of collection of each OP swab. Multiple imputation using chained equations will be used to impute missing viral load data prior to AUC calculation. Five data sets will be imputed, and imputed values will be calculated using non-missing viral load on each of the 7 sample collection days, treatment arm, age, sex, and whether or not a participant was hospitalized. A pooled linear regression model will be fit to log-transformed AUC as a function of treatment, age, and sex using the 5 imputed data sets. Difference in AUC by treatment arm and corresponding 95% confidence intervals will be reported using Rubin's Rules. The difference in AUC by treatment arm will also be done after refitting the model without participants who were hospitalized to assess sensitivity of results.

The incidence of hospitalizations and emergency department visits will be estimated for each arm, with 95% confidence intervals.

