5. CRITERIA FOR EVALUATION

5.1. Primary efficacy endpoint

- Time to first of two consecutive negative oropharyngeal tests for SARS-CoV-2 by qRT-PCR.

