6.2 Inclusion Criteria

Patients must fulfill all of the following inclusion criteria to be eligible for the study:

1. Age \geq 18 years and \leq 75 years at the time of the assessment
2. Able and willing to understand the study, adhere to all study procedures, and provide written informed consent
3. Diagnosis of COVID-19 disease:
 - a. If symptomatic, presence of mild to moderate symptoms without signs of respiratory distress, with FDA-cleared molecular diagnostic assay positive for SARS-CoV-2 within 72 hours from swab to the time of commencing informed consent:
 - b. If asymptomatic, initial diagnosis of SARS-CoV-2 infection with positive FDA-cleared molecular diagnostic assay obtained no more than 72 hours from initial swab to the time of commencing informed consent

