## 2.5 Exploratory efficacy analyses

An alternative definition of the secondary endpoint of symptom resolution will be considered in an exploratory analysis. We will evaluate time to sustained symptom resolution, defined as time from randomization until the first day in which no symptoms are reported and are not reported for the duration of the study. The analysis of time to sustained symptom resolution will follow the methods described for the secondary endpoint evaluation symptom resolution in the previous section. Time to symptom resolution based on symptom subsets (i.e. respiratory, systemic) will be similarly analyzed, additionally excluding participants who did not report symptoms from the specified subset at screening.

Time to disease progression will be defined as the time from randomization until the first day of a two point or more increase in either cough or shortness of breath persisting for at least 48 hours or an increase to a score of 4 or 5, or first day of admission to the emergency department, hospitalization, or death. Analysis and reporting of results will be done following methods detailed for time to symptom resolution.

Freedom from SARS-CoV-2 infection by oropharyngeal and nasal swabs at Day 5, 7, 10, and 14 will be modeled using a multivariable logistic regression model adjusted for age and sex. The odds ratio will be presented along with its 95% confidence interval.

Similar approaches to those used for evaluating SARS-CoV-2 viral load in oropharyngeal tests over time and AUC will be used to evaluate viral load in nasal tests.

Correlation between virology and symptomology will be characterized by evaluating the relationship between CT values obtained from the oropharyngeal tests and each symptom through two main approaches. For symptoms graded on an ordinal scale, we will calculate a Spearman correlation and assess significance with a Z-test. For variables that capture presence of a symptom, differences in the median CT values by presence or absence of the symptom will be presented and assessed via a Wilcoxon rank sum test.

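### SAP 2.4 scores symptom resolution on one unconfirmed symptom-free day in all randomized patients, so a transient good day, or the days before symptoms begin, can count as recovery

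*SAP*

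**What the plan says.** SAP 2.4 defines time to resolution of all symptoms as "the time from randomization until the first study day in which no symptoms are reported". It is analysed with Kaplan-Meier curves and a Cox model adjusted for age and sex. SAP 2.1 sets the population: "All efficacy analyses will be completed in the ITT population".

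SAP 2.5 adds a durable version, "the first day in which no symptoms are reported and are not reported for the duration of the study", and gives its status: "An alternative definition of the secondary endpoint of symptom resolution will be considered in an exploratory analysis".

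Participants without symptoms can enrol. Protocol 6.2 has a separate entry route for them: "If asymptomatic, initial diagnosis of SARS-CoV-2 infection with positive FDA-cleared molecular diagnostic assay". SAP 3 has one rule for them: "Participants who are asymptomatic at screening and never report symptoms thereafter will be considered to have met symptom resolution at study Day 1". It has no rule for those who develop symptoms later.

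Protocol 5.2 defines the endpoint for symptomatic patients only, with every symptom absent or mild, and asks for no confirming day either. Protocol 12.4 places the analysis in the subgroup symptomatic at baseline. Protocol 9.1.1 has participants complete a symptom questionnaire every day through Day 28.

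**The concern.** Symptoms can fluctuate from day to day. Under SAP 2.4 one blank questionnaire closes the record, whatever is reported the next day. Elsewhere the plan guards against this. Protocol 5.1 uses "Time to first of two consecutive negative oropharyngeal tests for SARS-CoV-2 by qRT-PCR", and one route to disease progression in SAP 2.5 is a "two point or more increase in either cough or shortness of breath persisting for at least 48 hours". The symptom endpoint has no such guard.

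There is a second gap. For a participant asymptomatic at screening who falls ill later, SAP 3 is silent and the wording of SAP 2.4 applies by default. That wording gives a resolution date before the illness starts.

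At stake are the reported times to symptom resolution, and the size and possibly the direction of the hazard ratio for a declared secondary endpoint.

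**Working it through.** **No figure to reproduce.** The documents give no power, event rate or hazard ratio for symptom resolution. The sizing in SAP 4.2 concerns shedding only.

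**Step 1: apply the wording to three hypothetical records.**

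| Record | SAP 2.4 date | Illness ends |
|---|---|---|
| Symptoms Days 0-5, none Day 6, cough Days 7-14, none from Day 15 | Day 6 | Day 15 |
| Asymptomatic at screening and Days 1-2, symptoms Days 3-10, none after | Day 1 | Day 11 |
| Symptoms Days 0-8, none after | Day 9 | Day 9 |

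The second record does not meet the SAP 3 condition for a Day 1 event, because symptoms are reported later. It still gets Day 1 from SAP 2.4. Protocol 5.2 and 12.4 would leave this record out.

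**Step 2: times.** In any complete diary the first symptom-free day is never later than the first of two consecutive symptom-free days. So stray symptom-free days can only shorten the recorded time.

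**Step 3: hazard ratio by hand.** Assume a constant recovery hazard *h* in control, true hazard ratio *R*, and a daily chance *q* of a stray symptom-free report while ill, so that λ = −ln(1 − *q*). The event is whichever comes first, hence

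observed HR ≈ (*R·h* + λ_active) / (*h* + λ_control).

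Assumed inputs: control median 10 days, so *h* = ln 2 / 10 = 0.0693; *R* = 1.7, so *R·h* = 0.1178; λ = 0.0202, 0.0513 and 0.1054 for *q* = 2%, 5% and 10%.

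Equal *q* in both arms:
- 2%: (0.1178 + 0.0202) / (0.0693 + 0.0202) = 1.54
- 5%: (0.1178 + 0.0513) / (0.0693 + 0.0513) = 1.40
- 10%: (0.1178 + 0.1054) / (0.0693 + 0.1054) = 1.28

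Unequal *q*:
- *R* = 1.7, control 5%, active 10%: 0.2232 / 0.1206 = 1.85, above the truth
- *R* = 1.7, control 10%, active 5%: 0.1691 / 0.1747 = 0.97, effect lost
- *R* = 1, control 5%, active 10%: 0.1747 / 0.1206 = 1.45, an apparent effect where recovery does not differ

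**Step 4: simulated daily diaries.** Assumed: 54 symptomatic patients per arm, Weibull recovery times (shape 1.8), control median 10 days, true HR 1.7, 3% chance per day of a stray symptom after recovery, 28 days, equal *q* in both arms. HR and power are from a Cox model.

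| *q* per day | Scored before recovery | Control median (days) | Single-day HR | Single-day power |
|---|---|---|---|---|
| 2% | 16% | 9.1 | 1.55 | 59% |
| 5% | 34% | 7.4 | 1.37 | 36% |
| 10% | 55% | 5.4 | 1.27 | 23% |

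With no stray days the control median is 10.6 days and the HR about 1.72. With two consecutive days, over the same range of *q*, HR is about 1.65 to 1.71, power about 68% to 76%, and 2%, 6% or 15% are scored early. Repeat runs moved the power figures by up to about six points.

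With no true effect and *q* of 5% control against 10% active, the Cox HR was about 1.44 under the single-day rule and 1.08 under the two-day rule.

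**Step 5: Day 1 scoring alone.** In a separate simulation without stray days, scoring an assumed 10% of participants in each arm as resolved on Day 1 took a true HR of 1.5 to about 1.44, and 2.0 to about 1.81.

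**The case against.** - **The SAP foresaw the problem.** Sustained resolution is pre-specified with the same methods, so readers will see both results. This stands in part. But the durable version is exploratory, and it errs the other way: one isolated symptom late in follow-up moves the date to the end. With 3% stray symptoms per day after recovery, it gave an HR of only about 1.2 against a true 1.7.
- **Every size is assumed.** This stands. Because the endpoint requires that no symptom at all be reported, an isolated blank day while ill may be uncommon. With no stray days the two rules perform alike.
- **Two days may not be enough.** The simulation treats stray days as independent. If remissions last several days, the two-day rule repairs less than shown. This stands.
- **Pre-symptomatic scoring is a gap, not a stated rule.** This stands. It follows from reading SAP 2.1, 2.4 and 3 together, and the protocol's restriction would remove it.
- **A reader might infer that the hazard ratio must shrink toward 1.** The documents do not support that. It needs stray symptom-free days to be equally frequent in both arms, and nothing in either document says so. A treatment that eases symptoms could change their frequency, and Step 3 shows inflation, loss of effect or a spurious effect.

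**Conclusion.** The point holds in conditional form. The declared secondary endpoint rests on one unconfirmed day. The SAP's population conflicts with Protocol 5.2 and 12.4, and later-onset participants are scored before their illness. Any stray symptom-free days make reported times to resolution too short. The hazard ratio may be biased: toward 1 if such days are non-differential, in either direction if not.

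The figures illustrate sensitivity and do not predict this trial's result. They rest on the assumed recovery times, effect, numbers and diary noise listed above.

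The stronger readings, that the result will be biased toward no effect or that the trial's main conclusion is at risk, are not supported. The primary endpoint does not use symptom data. This is a cheap improvement.

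**What to change.** In SAP 2.4, define the event as the first of two consecutive completed daily questionnaires with no symptoms, dated at the first. State that a missing questionnaire does not count as symptom-free.

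Restrict the analysis to participants symptomatic at baseline, as Protocol 5.2 and 12.4 do. If all randomized patients are kept, count resolution only after symptom onset for those who become symptomatic later, and say so in SAP 3.

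Apply the two-day rule to the symptom-subset endpoints in SAP 2.5. Keep the single-day and sustained versions as sensitivity analyses.

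The cost is SAP wording only, since the daily questionnaires are already collected. The downside is small: a first symptom-free day on Day 28 cannot be confirmed and is censored.
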